Thirty persons with MS will be randomized to either placebo or smoked cannabis. Patients will be assessed before and after treatment for 3 consecutive days (phase I); undergo wash out for a total of 11 days; and then cross over to either placebo or active treatment (phase II) depending on what they received during Phase I. Since each phase of treatment requires 2 assessments (before and after inhaled product) on each of 3 consecutive days, the study will allow comparisons to be made on spasticity, cognitive, neuropsychiatric, safety and global measures before and after treatment with cannabis or placebo for a total of twelve assessments. Blood will be drawn for quantitative analysis of serum THC before and immediately following each treatment session as an estimate of systemic exposure.

Considering start-up time, training and recruitment of personnel, procurement of equipment and supplies, and unanticipated initial delays, we expect that one-third (n=10) of the required subjects will be recruited and tested during the first year and that the remaining two-thirds (n=20) of the required subjects will be recruited and tested during the second year of the study.

The following schedule of visits is planned:

	Screening I	Screening II	PHASE I Treatment Days 1-3		Washout (Days 4-14)	PHASE II Treatment Days 15-17	
			B	A		B	A
Consent	x						
Eligibility Checklist	x	x					
Medical Hx/Screens	x						
Concomitant meds	x	x					
Urine Toxicology	x		x#			x#	x#
Adverse Events			x	x		x	x
EDSS		x					
Modified Ashworth Scale	x	x	x	x		x	x
Timed 25-ft Walk		x	x	x		x	x
Pain Analog Scale			x	x		x	x
Cognitive Battery		x	x	x		x	x
Neuropsychiatric Assessment		x	x	x		x	x
Tx Emergent Effects				x			x
MSQLI			x†	x†		x†	x†
Practice Session		x					
THC Assays			x	x		x	x

B=before treatment; A=after treatment; †=Days 1, 3 and 15, 17 only; #= Days 1,15, and 17 only

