Spasticity Scale, Timed 25-ft Walk, Visual Analog Scale of Pain, cognitive battery, neuropsychiatric assessments, and treatment-emergent effects, beginning 30 minutes after their treatment session. On the last day of the protocol, **Day #17**, the patients will return to the CRC for their third treatment of Phase II. Blood will be drawn for total THC. Patients will undergo assessment with the Modified Ashworth Spasticity Scale, Timed 25-ft Walk, Visual Analog Scale of Pain, cognitive battery, and neuropsychiatric assessments. Following completion of the third treatment, blood will be drawn for peak THC levels, and patients will be assessed with the Modified Ashworth Spasticity Scale, Timed 25-ft Walk, Visual Analog Scale of Pain, cognitive battery, neuropsychiatric assessments, treatment-emergent effects, and MSQL-I beginning 30 minutes after their treatment session.

2. Study Site

The study will be performed at the UCSD La Jolla Clinical Research Center. The CRC is a self-contained organized research unit that is fully staffed by nursing, dietary and core laboratory personnel to support the clinical research project described herein. A room will be equipped with a Tepco 750 smoke scrubber or a HEPA filter (BioSafety, RS 1000).

3. Subjects

We estimate that 30 subjects will be necessary (see Section 7) in this crossover design and therefore plan to enroll 36 MS subjects, expecting attrition of up to 6 subjects over the course of the study. MS patients will be obtained through the UCSD MS Clinic and/or the private practices of their neurologists. These patients will have received extensive neurological evaluation and represent a well-studied MS patient population. MS patients will be solicited by [name], and contacted for appointment by the Research Coordinator. Patients of all ethnic and racial backgrounds are eligible. Prior use of cannabis is not required. Patients will be allowed to continue other currently available treatments for spasticity other than benzodiazepines, if they have been on a stable dose of the medication for at least three months.

3.a. Inclusion Criteria

Subjects will be included if they:

- Have clinically definite or probable, laboratory-supported MS; are between the ages of 18-65

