6. Assessment Measures. Coincident with study aims, the following will be used to assess 1) spasticity and mobility; 2) cognitive, neuropsychiatric, and treatment-emergent features; 3) quality of life and global functioning:

Spasticity and Mobility (will be administered before and after each treatment session):

The **Modified Ashworth Scale** (Lee, 1989) is the most commonly used clinical measure of spasticity. Based on an evaluation of the degree of resistance to passive range of motion at one or more joints, it is an ordinal scale of muscle tone intensity (zero to 4): 1=no increase in tone; 1.5=slight increase in muscle tone, manifested by a catch, followed by minimal resistance throughout the remained (less than half) of the range of movement; 2=slight increase in tone, giving a catch when the limb is moved in flexion or extension; 3=more marked increase in tone,

Appendix to: [name], [name], [name], et al. Smoked cannabis for spasticity in multiple sclerosis: a randomized, placebo-controlled trial. *CMAJ* 2012. DOI:10.1503/cmaj110837.

Copyright © 2012 Canadian Medical Association or its licensors

but limb easily flexed; 4=considerable increase in tone, passive movement difficult; 5=affected part is rigid without any possible passive mobilization. Each assessment will involve ratings according to the Modified Ashworth Scale of the bilateral elbows, hips, and knees for a combined possible total point score of 30. **The Modified Ashworth Scale will be the primary outcome measure.**

The **Timed 25-Foot Walk Test** is a mobility and leg function performance test in which the patient is timed walking 25 feet. It is similar to the Ambulation Index, differing only with regard to scoring and is strongly recommended for clinical trials to examine ambulation and leg function.

The **Visual Analog Scale of the McGill Pain Questionnaire** is used to assess the intensity of pain. It is a 10-centimeter line anchored at one end by the descriptor "No Pain" and at the other by the words "Worst Pain Imaginable." The subject is asked to mark along the line indicating the severity of pain experienced; a score is derived by directly measuring the number of centimeters from the zero point to the subject's mark.

Cognitive, Neuropsychiatric, and Treatment-Emergent Effects):

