Assay for Total THC. Total THC will be determined using commercially available immunoassay in the UCSD Medical Center Laboratory of [name].

Urine Toxicology. Qualitative urine toxicology screens for nonprescribed substances will be obtained at screening, baseline for each phase, and study exit. The substances assayed will be amphetamines, ethanol, barbiturates, benzodiazepines, cocaine and benzoylecgonine, methadone, methaqualone, methylphenidate, phencyclidine, opioids, and tetrahydrocannabinol.

Carbon monoxide (CO). Exhaled CO levels will be measured by using an Ecolyzer. Expired CO levels before and after each treatment session will provide a measure of smoke exposure.

8. Statistical Considerations

Hypothesis #1: Smoking medicinal cannabis will result in improved scores on the Modified Ashworth Spasticity Scale and Visual Analog Scale of Pain compared to the placebo condition. Means and bootstrap-based bias-corrected confidence intervals will be computed for each assessment time of each specified measure. For each subject the response is the change between a before-after placebo difference and a before-after treatment difference on the specified measures. We will then evaluate the aggregate differences using a one-sample t-test (i.e. perform a paired-sample t-test). Here we define as clinically important any departure from zero in the hypothesized direction that is greater than one standard deviation of paired differences. A power analysis indicates that a sample size of 30 individuals will yield well over 80% power ($\alpha = 0.05$) to detect an effect of one SD; or greater. In addition the relationship between total plasma THC and spasticity scores will be examined using Pearson correlation.

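### The primary change-of-change score fixes the slope on the pre-dose Ashworth difference at one; adjusting for the matched pre-dose score is likely to be more precise

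*Protocol*

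**What the plan says.** Section D.6 names the endpoint: "The Modified Ashworth Scale will be the primary outcome measure". Section D.8, Hypothesis #1, fixes both the response and the test: "For each subject the response is the change between a before-after placebo difference and a before-after treatment difference on the specified measures", and then "We will then evaluate the aggregate differences using a one-sample t-test (i.e. perform a paired-sample t-test".

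Pre-dose scores are available in both phases. Section D.1 states: "Since each phase of treatment requires 2 assessments (before and after inhaled product) on each of 3 consecutive days". Section D.6 gives the same timing for the spasticity measures: "Spasticity and Mobility (will be administered before and after each treatment session".

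Section D.8 ends with regression and covariate analyses of association. Its examples are EDSS, smoking history, exhaled CO and concomitant medication. The pre-dose score is not among them, and the primary test is unchanged. For the quality-of-life inventory (Hypothesis #3) the same section compares post-treatment scores only, which is a slope of zero. It gives no reason for either slope.

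**The concern.** For each patient let D_post be the cannabis-minus-placebo difference in post-dose score and D_pre the same difference in pre-dose score. The planned response is D_post - 1 x D_pre.

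In a parallel-group trial a change score removes the patient's stable level. Here that level has already cancelled in the between-phase difference. What remains in D_pre is largely within-patient fluctuation and rating error, and the planned score subtracts all of it. If D_pre predicts D_post only moderately, the subtraction adds noise. Estimating the slope lets the data decide how much of D_pre to remove. At stake is the width of the primary confidence interval, and power for effects smaller than the planning value.

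**Working it through.** **The plan's own figure.** Section D.8 says 30 patients "will yield well over 80% power ($\alpha = 0.05$) to detect an effect of one SD" or more. For a one-sample t-test with n = 30 and an effect of 1 SD, the noncentrality is 1 x sqrt(30) = 5.48 on 29 df. Power is 99.96% two-sided and 99.99% one-sided (the protocol does not state which). The claim is reproduced. Ten patients would already give 80% two-sided, and with 30 patients 80% power is reached at 0.53 SD.

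**Variance formulas.** Let rho be the correlation between D_pre and D_post, and assume both have the same SD, s.

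- Planned score: 2s²(1 - rho)
- Slope estimated: s²(1 - rho²)
- Ratio: (1 + rho)/2
- Post-dose difference alone: s², which is smaller than the planned variance when rho is below 0.5

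**Finite-sample cost.** With n = 30 the estimated slope and the lost degree of freedom multiply the width by about sqrt(1 + 1/27) x 2.048/2.045 = 1.02. In simulation (40,000 runs per setting) the factor is 1.019. This is the whole result when the true slope is one.

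**Single matched session.** Width ratio, adjusted to planned, is 1.019 x sqrt((1 + rho)/2). The simulated values agree:

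| rho | sqrt((1 + rho)/2) | simulated ratio | simulated trials with a narrower interval |
|---|---|---|---|
| 0.3 | 0.806 | 0.82 | 97.5% |
| 0.5 | 0.866 | 0.88 | 92% |
| 0.7 | 0.922 | 0.94 | 77% |
| 0.9 | 0.975 | 0.99 | 46% |

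Break-even is at about 0.92-0.93.

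**Matched three-day average.** Assume that a share q (0 to 0.75) of the correlated variance is day-specific and that rating error is independent between ratings. Averaging three days gives a shared variance V = rho(1 - q) + rho x q/3 and an error variance (1 - rho)/3. The correlation of the averaged scores is r = V/(V + (1 - rho)/3).

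- rho 0.3: r = 0.15/0.383 = 0.39 (q = 0.75) to 0.30/0.533 = 0.56 (q = 0); width ratio 0.85 to 0.90
- rho 0.5: r = 0.25/0.417 = 0.60 to 0.50/0.667 = 0.75; width ratio 0.91 to 0.95
- rho 0.7: r = 0.35/0.45 = 0.78 to 0.70/0.80 = 0.875; width ratio 0.96 to 0.99

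The interval is thus 10-15%, 5-9% and 1-4% narrower. Break-even applies to r, the correlation of the scores actually entered.

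**Mismatched covariate.** If the outcome is the three-day average but the covariate is Day 1/Day 15 only, the adjusted variance is V + (1 - rho)/3 - V², against 2(1 - rho)/3 for the planned score. At rho 0.5 and q = 0 this is 0.500 + 0.167 - 0.250 = 0.417 against 0.333, so the width ratio is 1.019 x sqrt(1.25) = 1.14. Over the range of q the ratios are 0.90-0.99 at rho 0.3, 1.05-1.14 at 0.5 and 1.27-1.35 at 0.7. For a Day 3 outcome with a Day 1/Day 15 covariate they are 0.82-0.86, 0.88-1.01 and 0.94-1.29.

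**Power, single matched session, two-sided.** With effects in SDs of the planned score and rho of 0.3, 0.5 and 0.7, power at 0.53 SD rises from 80% to 93%, 89% and 85%. At 0.4 SD it rises from 56% to 73%, 67% and 62%. At 1 SD it stays at 99.96% or above.

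**The case against.** The planned test is valid, nothing in the protocol contradicts it, and its power claim is correct. On this view the choice of covariate is a refinement that an analysis plan could make. That stands as a limit on the importance of the point. But Section D.8 specifies both the response and the test, so the slope of one is a choice the protocol has made, not a detail it left open.

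The size cannot be known from the document. It gives neither rho nor any raw SD, and if the post-dose SD exceeds the pre-dose SD so that the true slope is one, adjustment gains nothing. This stands too. A reader might infer that adjustment is certain to narrow the interval and is free. The documents do not support that: even at rho 0.7 about a quarter of simulated trials had no narrower interval.

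Day 1 and Day 15 are tempting as covariates because no dose precedes them in the same phase. They are matched only to a Day 1/Day 15 outcome; otherwise they can widen the interval, as shown above. Nor is Day 15 guaranteed free of residual drug: Section D.1 provides for a positive cannabis screen that day, though this does not show a residual effect on spasticity.

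Last, adjustment can change the question. The planned contrast is mean(D_post) - mean(D_pre), and the adjusted intercept is mean(D_post) - b x mean(D_pre). They differ by (1 - b) x mean(D_pre), which is zero in expectation only if the pre-dose scores carry no treatment effect. On Days 2-3 and 16-17 those scores follow earlier doses in the same phase, so this must be stated as an assumption.

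**Conclusion.** The point holds as a likely loss of precision in the primary estimate. It rests on equal pre- and post-dose SDs, a matched pre-dose covariate and a correlation that the protocol does not give. Under those assumptions the gain in interval width ranges from about 18% (rho 0.3, one session) to about 1% (rho 0.7, three-day average). It disappears above a correlation of about 0.9 or with a true slope near one. The worst cost found for a matched covariate was about 2% in width.

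A reader might infer that the planned analysis is biased or invalid, or that the trial is underpowered. Neither follows: the paired t-test is a valid test of the contrast it defines, and power at the planned one SD exceeds 99.9% either way. The benefit is a tighter interval and better power for smaller effects. It is a desirable improvement, not a necessary correction.

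**What to change.** In Section D.8, Hypothesis #1, make the primary estimate the intercept, with its 95% CI, from a regression of the post-dose cannabis-placebo Ashworth difference on the pre-dose cannabis-placebo difference. Take the pre-dose difference from the same session or sessions that enter the planned change score: the same day, or the same average over days. Keep the paired t-test on the change-of-change score as a sensitivity analysis.

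Do not substitute Day 1/Day 15 pre-dose scores when the outcome is a three-day average or Day 3. If pre-dose scores from Days 2-3 and 16-17 are used, state that the intercept equals the planned contrast only if those scores carry no treatment effect.

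The cost is a few sentences and one of the 29 degrees of freedom. No new data or visits are needed.

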Screening visit I will include informed consent, systematic semi-structured interview of medical history, screen for substance abuse, psychiatric screen, review of concomitant medications, and completion of inclusion/exclusion criteria. The Substance Abuse Module of the Diagnostic Interview Schedule for DSM-IV will be administered to exclude individuals with current substance use disorders. A psychiatric screen will be conducted using the Screening Module of the Structured Clinical Interview for DSM-IV. Individuals reporting potential histories of anxiety, psychotic disorders, or substance dependence disorders will be interviewed using the appropriate module, and excluded if an Axis I diagnosis is established. The Beck Depression Inventory-II will also be administered (Beck et al 1996) and individuals who exceed a cut-off score of 17, suggesting mild depression, will be interviewed by a collaborating psychiatrist for mood disorder. Those with current mood disorder (dysthymia, major depression, bipolar disorder) will be

Appendix to: [name], [name], [name], et al. Smoked cannabis for spasticity in multiple sclerosis: a randomized, placebo-controlled trial. *CMAJ* 2012. DOI:10.1503/cmaj110837.
Copyright © 2012 Canadian Medical Association or its licensors

excluded. The Modified Ashworth Spasticity Scale will be administered. If the patient remains eligible, urine will be collected for toxicologic screen. A positive toxicologic screen for drugs of abuse including cannabis will exclude the patient from further participation.

Eligible patients will return for Screening visit II which must be within 7 days of Screening visit I. At Screening visit II, concomitant medications and inclusion/exclusion criteria will be reviewed. An Expanded Disability Status Scale (EDSS) score will be calculated for each patient. The EDSS rates disabilities experienced by MS patients on a zero to 10 scale and is a reliable and valid measure of impairment and disability (Coulthard-Morris, 2000). The Modified Ashworth Spasticity Scale, Timed 25-ft Walk, and cognitive battery will be administered to reduce subsequent practice effects. Patients will undergo a “practice session” with placebo product to ensure subsequent performance. **They will not be told that the practice session involves placebo.** Patients will be randomized to their treatment arm.

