Cognition will be assessed before and after each treatment session by means of the PASAT, WAIS-III Digit Symbol Subtest, Trail Making Test, and Hopkins Verbal Learning Test. The **PASAT** is a multiple computational task that is designed to measure attention and information processing speed. It measures how rapidly a person can perform numeric operations on digits held in short-term memory and provides an estimation of the amount of information a person can handle at one time. The **WAIS-III Digit Symbol Subtest** (Wechsler, 1997) is a test of psychomotor speed, concentration, and graphomotor abilities which requires the respondent to match symbols to numbers as quickly as possible. The **Trail Making Test** is a measure of psychomotor speed, attention and cognitive sequencing. The **Hopkins Verbal Learning Test** (Benedict et al, 1998) provides information on the ability to learn and immediately recall verbal information across trials, as well as the ability to retain, reproduce, and recognize this information after a delay 10-15 minutes. Six alternate forms of the test are available.

Neuropsychiatric symptoms will be assessed before and after each treatment session by the **Brief Symptom Inventory** (Derogatis, 1978) which is interpreted in terms of 9 primary symptom dimensions: somatization, obsessive-compulsiveness, interpersonal sensitivity, depression, anxiety, hostility, phobic anxiety, paranoid ideation, and psychoticism. It is a 53-item, self-report symptom inventory derived from the Symptom Checklist-90 Revised, which requires the patient to respond to each item in terms of a 5-point scale of distress, ranging from "not-at-all" to "extremely". Typically, it requires 10 minutes for patient completion.

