Hypothesis #2: Smoking medicinal cannabis will result in impairment on cognitive measures of attention, concentration, and memory in addition to adverse neuropsychiatric features as measured by the Paced Auditory Serial Addition Test, Brief Symptom Inventory, Perceived Deficits Questionnaire, Modified Fatigue Impact Scale, the Subjective Ratings of High and Sedation - Revised, and UKU Side Effect Rating Scale. Means and bootstrap-based bias-corrected confidence intervals will be computed for each assessment time of each specified measure. For each subject the response is the change between a before-after placebo difference and a before-after treatment difference on the specified measures where before and after treatment measurements were taken (e.g. PASAT), and a change between the post-placebo and post-active scores when only the post-treatment measurements were taken (e.g. SRHS-R). We will evaluate the aggregate differences using a one-sample t-test (i.e. perform a paired-sample t-test). Here again we define as clinically important any departure from zero in the hypothesized direction that is greater than one standard deviation of paired differences. In

Appendix to: [name], [name], [name], et al. Smoked cannabis for spasticity in multiple sclerosis: a randomized, placebo-controlled trial. *CMAJ* 2012. DOI:10.1503/cmaj110837.

Copyright © 2012 Canadian Medical Association or its licensors

addition the relationship between total plasma THC and cognitive, neuropsychiatric and treatment-emergent effect scores will be examined using Pearson correlation.

Hypothesis #3: Smoking medicinal cannabis will result in improvement in global abilities and quality of life as measured by the Multiple Sclerosis Quality of Life-Inventory. For each subject the response is the change between a post-placebo and a post-treatment score on the MSQOL-I. The aggregate differences will be evaluated using a one-sample t-test (i.e. perform a paired-sample t-test).

Regression and covariate analysis will also be applied to determine the association between the major efficacy/safety outcomes and important clinical variables such as EDSS score, smoking history, exhaled CO levels, concomitant medications, etc.

E. HUMAN SUBJECTS

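### The protocol analyses a two-period crossover with a pooled paired t-test that leaves out period; adjusting for period costs one degree of freedom and should be adopted, although the stated sample size is not undermined

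*Protocol*

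**What the plan says.** Section D.1 of the protocol describes a randomised, placebo-controlled crossover with two three-day phases separated by an eleven-day washout. Patients therefore receive cannabis then placebo, or placebo then cannabis.

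Section D.8 fixes the analysis. For Hypothesis 1, which covers the primary Modified Ashworth outcome, "For each subject the response is the change between a before-after placebo difference and a before-after treatment difference on the specified measures". The test follows: "We will then evaluate the aggregate differences using a one-sample t-test (i.e. perform a paired-sample t-test". Hypothesis 2 repeats it: "We will evaluate the aggregate differences using a one-sample t-test (i.e. perform a paired-sample t-test". There, measures taken only after treatment (the protocol's example is the SRHS-R) enter as post-placebo against post-active scores. Hypothesis 3 compares post-placebo with post-treatment MSQLI scores by the same test.

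None of the three contains period or sequence. The closing regression sentence of D.8 lists EDSS, smoking history, exhaled CO and concomitant medications as examples of covariates, but not period.

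Clinical importance is defined as "any departure from zero in the hypothesized direction that is greater than one standard deviation of paired differences". On sample size: "A power analysis indicates that a sample size of 30 individuals will yield well over 80% power". That statement rests on an alpha of 0.05 and a target effect of at least one SD.

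The protocol recognises order effects. At Screening visit II the Ashworth scale, the timed walk and the "cognitive battery will be administered to reduce subsequent practice effects". For the Hopkins Verbal Learning Test, section D.6 says: "Six alternate forms of the test are available".

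**The concern.** Patients are randomised to an order of treatments, and the pooled paired t-test discards that order. If the response differs between Phase I and Phase II for reasons other than treatment, the difference is added to the active-minus-placebo contrast in one sequence and subtracted in the other. With equal sequences this becomes extra variance. With unequal sequences part of it becomes bias.

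Such effects are plausible here. One practice administration can reduce practice effects but need not remove them, and twelve assessments follow. The Hopkins test would be given 1 + 12 = 13 times with six forms, so forms must repeat.

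Unequal sequences are plausible too. Section D.3 allows for losing up to 6 of 36 patients. The Day 15 exclusion in D.1 refers back to the Day 3 THC level, which depends on sequence, so losses need not fall evenly.

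At stake are the accuracy of the estimates and confidence intervals, chiefly for the cognitive and tolerability measures of Aim 2, and the meaning of the one-SD threshold.

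**Working it through.** **1. The plan's own figure.** Inputs from D.8: n = 30, effect = 1 SD of paired differences, alpha = 0.05. Sidedness is not stated, so both were tried. The power of a one-sample t-test follows from the noncentral t with 29 degrees of freedom and noncentrality 1 × √30 = 5.48. This gives 99.96% two-sided and 99.99% one-sided, consistent with the stated power. With 80% power and a two-sided test, 30 patients can detect 0.53 SD. I use 0.53 SD below as a more sensitive yardstick; it is not the protocol's target.

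**2. How period enters.** Let τ be the treatment effect and P the period difference (Phase II minus Phase I) in the response. Both are in units of σ, the within-sequence SD of the active-minus-placebo differences. The expected difference is τ − P in cannabis-first patients and τ + P in placebo-first patients. With n1 placebo-first, n2 cannabis-first and N = n1 + n2:

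- bias of the pooled mean = P(n1 − n2)/N
- pooled SD = σ√[1 + P² × (4n1n2/N²) × N/(N − 1)]

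For 15/15 and P = 0.5, bias = 0 and SD = √(1 + 0.25 × 30/29) = 1.122. For 18/12 and P = 0.5, bias = 0.5 × 6/30 = 0.10 SD. For 20/10 and P = 0.5, bias = 0.5 × 10/30 = 0.167 SD.

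**3. The period-adjusted alternative.** The estimate is the average of the two sequence means, with SE = (σ/2)√(1/n1 + 1/n2) and N − 2 degrees of freedom. It is unbiased for any additive P. The SE is 0.1826 at 15/15 (the same as 1/√30), 0.1863 at 18/12 and 0.1936 at 20/10.

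**4. Simulated rejection rates** (two-sided 0.05, N = 30, P = 0.5 SD assumed, at least 100,000 trials per cell). Where two figures are given, the first is with the bias against cannabis and the second with it in favour.

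| Sequences | Bias (SD) | Null rejection, paired | Power at 0.53 SD, paired | Power at 0.53 SD, adjusted | Power at 1 SD, paired |
|---|---|---|---|---|---|
| 15/15 | 0 | 2.9% | 73% | 80% | 99.9% |
| 18 and 12 | ±0.10 | 5.3% | 53% or 87% | 78% | 99.5% or above 99.9% |
| 20 and 10 | ±0.17 | 10% | 40% or 93% | 75% | 98.7% or above 99.9% |

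At P = 0.25 SD the effects are smaller. At 15/15 the SD rises by 3%, null rejection is about 4.3% and power at 0.53 SD is about 78%. At 18/12 the bias is 0.05 SD and null rejection about 5.1%. Null rejection under the adjusted test stays near 5% throughout.

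**5. How likely is imbalance?** The allocation method is not stated, so two assumptions bracket it. Starting from 18/18 with six random losses, an 18/12 split needs all six from one sequence (probability 1.9%); 17/13 or worse has probability 17.7%. Under simple 1:1 allocation of 30 patients, a gap of 6 or more has probability 36% and a gap of 10 or more about 10%.

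**6. Which measures are exposed?** For a before-after response, a level shift common to both assessments of a phase cancels. Only a phase difference in the within-session change survives, such as a practice gain that shrinks with repetition. For post-only responses (SRHS-R, UKU, MSQLI) a level shift enters in full.

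**The case against.** The strongest defence is that the primary response is already a difference of before-after changes, which removes any constant shift between phases. That stands. The practice evidence also concerns mainly the cognitive tests. The Hopkins test is not in the list of measures under Hypothesis 2 in D.8, and although the Ashworth scale gets a practice run, nothing in the protocol points to a remaining phase effect on the Ashworth change. A reader might infer that the primary estimate will mix treatment with practice; the protocol does not support that.

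A reader might also infer that the trial is underpowered or prone to false positives. At the protocol's own one-SD target the paired test keeps about 99% power. The fall to 53% arises at 0.53 SD and only when the bias runs against cannabis; reversed, power is 87%. Type I error rises materially only with marked imbalance, and with equal sequences the test errs on the conservative side. An 18/12 split is also unlikely if allocation is balanced and losses are random.

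Finally, a separate analysis plan might add period. But the protocol does not leave the test open: it names one for each hypothesis, and that test has no period term. The core point therefore survives, at reduced weight.

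**Conclusion.** The point holds as a should-fix. The named test does not match the crossover design: it leaves any period effect in the error term and, with unequal sequences, in the estimate. At an assumed period effect of 0.5 SD, equal sequences give no bias but an SD about 12% too large, which raises the one-SD importance threshold by the same proportion. An 18/12 split gives a bias of 0.10 SD in either direction. Only at about 20/10 does null rejection reach roughly 10%.

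These sizes rest on an additive period effect of 0.25 to 0.5 SD, for which the protocol gives no figure, and on a sequence imbalance that it does not specify. The exposure is greatest for the cognitive tests and the post-only scores, and probably small for the examiner-rated Ashworth score. The documents do not support a claim that the primary conclusion or the sample size of 30 is threatened at the stated target.

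**What to change.** In D.8, under Hypotheses 1 to 3, replace the one-sample (paired) t-test by a period-adjusted crossover analysis. Either of these will do:

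- a two-sample comparison of period differences between the sequences, with half that contrast as the treatment estimate (Hills-Armitage); or
- a linear mixed model with treatment and period as fixed effects and patient as a random effect.

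Compute the standard deviation for the one-SD importance threshold within sequence, so that a period effect cannot move it.

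The cost is one degree of freedom and a change of wording; no further data or patients are needed. If there is no period effect, power at 0.53 SD is unchanged at 80% for 15/15 and falls to about 78% for 18/12 and 75% for 20/10. Power for one SD stays at 99.9% in all three.
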